- b) **Executive Function:** We will measure executive function using a behavioral task. *Hypothesis:* Compared with healthy control participants, patients with psychotic disorders will have executive dysfunction, as measured by a higher number of errors and longer reaction times on both tasks, both at baseline and after sham TMS. We predict that these deficits in patients will become more exaggerated after inhibitory TMS, and improve after excitatory TMS.
- c) **Symptoms:** We will measure mood and psychotic (e.g., hallucinations, delusions) symptoms with visual analogue scales (VAS). *Hypothesis:* Symptom ratings will improve in the period immediately after excitatory TMS, and worsen in the period immediately after inhibitory TMS, and show no significant change after sham TMS.

Aim 2: Investigate the relationship between time perception and (a) executive function and (b) symptomatology in patients with psychotic disorders. Hypothesis: We hypothesize that performance on the time perception task will correlate with performance on a working memory task as well as with mood and psychotic symptoms.

III. SUBJECT SELECTION:

We will recruit participants from the following two groups:

1. **Patients with psychotic disorders** – patients diagnosed with schizophrenia (SZ), schizoaffective disorder (SZA), or psychotic bipolar disorder (BP).
2. **Healthy controls (HC)**—individuals with no psychiatric illness.

We will enroll up to 100 participants for each of the two protocols (Protocol A and Protocol B, which are identical except that they involve different time perception and executive tasks that participants must complete before and after the cerebellar TMS. Specifically, the tasks in Protocol A are the interval discrimination task, flanker task and the N-back working task, while those in Protocol B are the repetitive finger tapping task and the Multi-Source Interference Task, or MSIT). Participants may elect to participate in both Protocol A and Protocol B, should they wish to do so. Participation in the second protocol will be entirely optional.

Protocol A:

n=50 patients with psychotic disorders
 n=50 healthy controls

Protocol B:

n=50 patients with psychotic disorders
 n=50 healthy controls

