assessments pre- and post-TMS require input solely from the subjects. However, subjects will be blinded as to which mode of TMS they receive at each study visit. Sham TMS will use the exact same procedure with a sham coil, which is designed to induce the same nonspecific sensory effects of TMS (auditory and somatosensory activation) without inducing the neuromodulatory magnetic fields. At the end of each study visit, subjects will be asked to speculate on which mode of TMS (inhibitory, excitatory, or sham) they received as well as the degree of certainty of their judgment so that we can assess the potential contributions of subjects' expectations on their task performance.

V. STUDY PROCEDURES:

All subjects, including healthy controls, will undergo three visits at the MGH Laboratory for Neuropsychiatry and Neuromodulation in the Charlestown Navy Yard Campus, with at least 36 hours separating the visits.

The subject is free to withdraw from the study at any time simply by informing the investigators. Similarly, the investigators may decide to stop the study if the purposes of the study cannot be met (technical difficulties, new information on subject characteristics, etc.).

Summary of Study Procedures

The first visit will include the following procedures (for the second and third visits, the clinical characterization step will be skipped):

Patients:

- Consenting procedures (15-20 minutes)
- Clinical characterization (1-2 hours)
 - Positive and Negative Syndrome Scale (PANSS)
 - Young Mania Rating Scale (YMRS)
 - Montgomery-Asberg Depression Rating Scale (MADRS)
 - North American Adult Reading Test (NAART)
 - Psychotic Symptom Rating Scale: PSYRATS-AH
 - The Behavior Rating Inventory of Executive Function – Adult Form (BRIEF-A)
 - Barratt Impulsiveness Scale (Version 11; BIS-11)
 - Fagerstrom Test for Nicotine Dependence
- Urine toxicology/pregnancy screen (5 minutes)
- Baseline/pre-TMS assessments (15-20 minutes)
 - Interval discrimination task for Protocol A (or repetitive finger-tapping task for Protocol B)
 - N-back working memory task for Protocol A (or multi-source interference task (MSIT) for Protocol B)
 - Flanker task for Protocol A
 - Visual analog scales (VAS) to assess mood and psychotic symptoms
- Transcranial Magnetic Stimulation (TMS) (15 minutes)
 - Excitatory, inhibitory, or sham (order randomized)
- Post-TMS assessments (15-20 minutes)
 - Interval discrimination task for Protocol A (or repetitive finger-tapping task for Protocol B)

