 - N-back working memory task for Protocol A (or multi-source interference task (MSIT) for Protocol B)
 - Flanker task for Protocol A
 - Visual analog scales (VAS) to assess mood and psychotic symptoms

Healthy Control Participants:

- Consenting procedures (15-20 minutes)
- Clinical characterization (1-2 hours)
 - Structured Clinical Interview for DSM-IV-TR (SCID)
 - North American Adult Reading Test (NAART)
 - The Behavior Rating Inventory of Executive Function – Adult Form (BRIEF-A)
 - Barratt Impulsiveness Scale (Version 11; "BIS-11")
 - Fagerstrom Test for Nicotine Dependence
- Urine toxicology/pregnancy screen (5 minutes)
- Baseline/pre-TMS assessments (15-20 minutes)
 - Interval discrimination task for Protocol A (or repetitive finger-tapping task for Protocol B)
 - N-back working memory task for Protocol A (or multi-source interference task (MSIT) for Protocol B)
 - Flanker task for Protocol A
 - Visual analog scales (VAS) to assess mood and psychotic symptoms
- Transcranial Magnetic Stimulation (TMS) (15 minutes)
- Visual analog scales (VAS) to assess mood and psychotic symptoms
 - Excitatory, inhibitory, or sham (order randomized)
- Post-TMS assessments (15-20 minutes)
 - Interval discrimination task for Protocol A (or repetitive finger-tapping task for Protocol B)
 - N-back working memory task for Protocol A (or multi-source interference task (MSIT) for Protocol B)
 - Flanker task for Protocol A
 - Visual analog scales (VAS) to assess mood and psychotic symptoms

Clinical characterization

For the purposes of clinical characterization, we will record demographic (i.e. age, sex, race/ethnicity, parental education, duration of illness, handedness) and medication information for all subjects during the first visit. For healthy control participants, we will administer the SCID, which assesses lifetime history of psychiatric symptoms and diagnoses, but not symptom severity, which can fluctuate over time. To capture the clinical presentation of patients at the time of the study, we will use the following clinical scales (included with this protocol): PANSS, YMRS, MADRS, PSYRATS-AH, BRIEF-A, BIS-11. Each of these scales will be used to capture the most severe symptoms in the previous month. The NAART, BRIEF-A, BIS-11, will be administered for all subjects. The clinical characterization step will not be repeated at study Visits 2 and 3 for either Protocol A or B.

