Once the MT is determined, we will apply TBS to our main target: the **cerebellar vermis**. In specific, we will target the posterior vermis (comprised of lobules VI-X), which is believed to subserve cognitive and affective functions (vs. the anterior vermis, comprised of lobules I-V, which is associated with somatomotor functions). From a practical standpoint, the posterior vermis (especially lobules VII-VIII) is also closer to the skull surface and thus will receive more direct TMS modulation (**Figure 4**). Using the Localite TMS neuronavigation system we will co-register the participant's head to his or her MRI, and place the TMS coil over the scalp position that allows direct stimulation of the vermal lobules VII-VIII in the mid-sagittal plane.

[figure not shown]

Figure 4. Mid-sagittal view of the cerebellum. We will apply theta-burst stimulation (TBS) to the posterior cerebellar vermis, directing the coil to lobules VII and VIII, which are closest to the skull surface. Figure from ¹¹³, pp. 241, figure 4.

At this point, the experimental session can begin. In a random order, patients will receive either cTBS (inhibitory), iTBS (excitatory) or sham TBS in each of the 3 sessions. Subjects will be blinded as to which mode of TMS they receive at each study visit. Sham TMS will use the exact same procedure with a sham coil, which is designed to induce the same nonspecific sensory effects of TMS (auditory and somatosensory activation) without inducing the neuromodulatory magnetic fields. At the end of each study visit, subjects will be asked to speculate on which mode of TMS (inhibitory, excitatory, or sham) they received as well as the degree of certainty of their judgment so that we can assess the potential contributions of subjects' expectations on their task performance.

Visual Analogue Scales (VAS)

A visual analogue scale (VAS) is a psychometric response scale, which easily and rapidly allows subjects to self-evaluate the intensity of subjective measures, such as mood and psychotic symptoms. Participants will complete visual analogue scales to indicate their current levels of

depression, anxiety, euphoria, auditory hallucinations, visual hallucinations, paranoia, referential thinking, and delusions of control before and after TMS using RedCap.

Behavioral Tasks

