To protect the subjects from the risk of a seizure, this study strictly adheres to the international safety consensus by using only TMS parameters that have never induced seizures in healthy subjects and by excluding subjects at increased risk for seizures (Rossi et al., 2009). In the unlikely event that a seizure occurred, the seizure would stop as soon as the TMS was stopped, and the MGH TMS clinical service safety plan would be activated, including transfer of the subject with an ambulance to MGH ER for a medical check-up. No one has ever developed epilepsy as a consequence of TMS. There are no known or foreseeable long-term risks associated with TMS.

Subjects are thoroughly screened by a research assistant prior to their enrollment in the study to ensure subject safety. Subjects are carefully assessed before, during, and after TMS administration by study staff to ensure that they suffer no adverse reactions.

Psychosocial risks

Answering questions about psychiatric history and symptoms during the psychiatric evaluation may cause anxiety or discomfort. However, patients will not be forced to answer any questions, will be given multiple opportunities to take breaks, and may completely withdraw from the study without any negative consequences. The risk of breach of confidentiality is present by extremely slight, given the precautions we take in de-identifying and protecting our data. The subject may feel mildly bored or frustrated while participating in the behavioral tasks, but he or she is free to stop at any time.

Though we anticipate no increase in risk of suicide or self-harm as a result of study procedures or participation, we are (a) studying psychiatric patients and (b) our study procedures involve asking participants about mood and psychosis symptoms at each of the study visits. Therefore, it is possible that in the course of study participation, participants may have and/or express suicidal ideation or intent. If a research staff has any concerns about participant suicidality during a study visit, the research team will follow the plan outlined below:

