PROTOCOL TITLE

Cerebellar transcranial magnetic stimulation (TMS) in psychotic disorders: effect on time perception, executive function, and mood and psychotic symptoms

NCT Number: NCT02642029

Date: August 22, 2022

Statistical Analyses:

We will test for group differences in demographic and clinical variables using χ^2 and t-tests or ANOVA, as appropriate. To examine the effect of TBS conditions on symptoms (as measured by visual analog scale scores, which are not normally distributed), we will conduct the non-parametric Friedman's test. For all other outcome measures, we will use mixed model regressions with TMS condition (cTBS, iTBS, or sham TBS), time (pre-TMS, post-TMS), and the interaction of condition x time as the primary variables of interest. To test the association between performance on the interval discrimination task (IDT) and symptoms, we will run mixed model regression models with TMS condition and time in addition to symptom score as the primary variable of interest.

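### The IDT-symptom model names no visit term, so a visit shift shared by the IDT and the VAS could enter the Aim 2 slope; stating one is a nearly free improvement

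*SAP*

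**What the plan says.** The SAP (Statistical Analyses) gives the association model in one sentence: "we will run mixed model regression models with TMS condition and time in addition to symptom score as the primary variable of interest". For the other non-VAS outcomes it lists TMS condition, time (before or after TMS) "and the interaction of condition x time as the primary variables of interest". Neither sentence mentions visit, period or sequence, and neither does the ANOVA or covariate list in Protocol VI.C. Both SAP sentences list variables of primary interest, and no full covariate or random-effects structure is given.

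The SAP does not name the symptom score in the association model. Two sentences earlier it refers to "symptoms (as measured by visual analog scale scores, which are not normally distributed", so the VAS is the natural reading. Protocol V has participants rate "depression, anxiety, euphoria, auditory hallucinations, visual hallucinations, paranoia, referential thinking, and delusions of control before and after TMS using RedCap". The alternative would be a clinical scale recorded once per protocol, of which Protocol V (Clinical characterization) says "Each of these scales will be used to capture the most severe symptoms in the previous month".

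Aim 2 (Protocol II) hypothesises that "performance on the time perception task will correlate with performance on a working memory task as well as with mood and psychotic symptoms". The IDT is used in Protocol A only, before and after TMS at each of three visits. The order of TMS conditions is randomised per subject (Protocol IV).

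**The concern.** Randomising the order protects comparisons between TMS conditions from visit effects. It does not protect a regression of one measured outcome on another. If IDT performance and VAS ratings both differ systematically between visits, the two series move together even when a person's symptoms and timing are unrelated. Neither condition nor pre/post time absorbs this: condition is independent of visit by design, and every visit has both a pre and a post score.

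The documents make a Visit 1 shift in the VAS plausible. Clinical characterisation takes 1-2 hours and, in Figure 2, comes before the VAS and tasks at Visit 1, whereas "for the second and third visits, the clinical characterization step will be skipped". Protocol VII warns that "Answering questions about psychiatric history and symptoms during the psychiatric evaluation may cause anxiety or discomfort", and anxiety is a VAS item. For the IDT, the task is repeated six times with one fixed trial order (Protocol V, Behavioral Tasks), so a practice or first-visit shift is possible, but no passage reports one.

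At stake is whether an IDT-symptom association, in either direction, could reflect only the difference between Visit 1 and later visits.

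**Working it through.** **The plan's own figure.** The documents give no figure for the association. The only power statement (Protocol VI.D) is 80% for an effect of 0.35 with 50 patients. Φ(0.35 × √50 − 1.645) = Φ(0.830) = 79.7%, so it reproduces at a one-sided 5% level; at two-sided 5% it is Φ(0.515) = 69.7%. Nothing below rests on it.

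**Inputs.** From the documents: 50 patients, three visits, pre and post scores at each (six pairs per patient), randomised order. Assumed: two-sided 5%, intraclass correlation 0.6 for both measures, true slope 0, and all shift sizes, in units of the within-subject SD.

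**Slope by hand.** A step of size d at one of three visits has variance d² × (1/3) × (2/3) = 2d²/9. With steps d_V in the VAS and d_I in the IDT, the within-person slope without a visit term is

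(2 d_V d_I / 9) / (1 + 2 d_V² / 9).

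With the simulated standard error of about 0.058, the approximate false-positive rate is P(|Z + slope/0.058| > 1.96). For equal steps d, in opposite directions in the simulation (the sign does not affect the rate):

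| d | slope by formula (absolute) | slope / 0.058 | implied rate | simulated, no visit | simulated, visit added |
|---|---|---|---|---|---|
| 0.2 | 0.009 | 0.15 | 5.3% | 5.0% | 4.3% |
| 0.3 | 0.020 | 0.34 | 6.3% | 6.8% | 5.0% |
| 0.5 | 0.053 | 0.91 | 14.8% | 14.4% | 5.6% |
| 0.7 | 0.098 | 1.69 | 39.5% | 37.9% | 6.0% |

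The simulation used 3,000 runs per row (Monte Carlo error about 0.4 points near 5%) and a random-intercept model. A second set of runs gave 5.6% at 0.3, 14.4% against 4.5% at 0.5, and 38% against 5% at 0.7. With 40 usable patients, a step of 0.5 gives 11.2% against 5.3%.

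**When it does not bite.** All without a visit term:
- IDT shifts alone: 4.7%. VAS shifts alone: 5.3%.
- Symptom score fixed within subject (a once-only scale): 5.5%.
- Unequal steps, VAS 0.5 and IDT 0.2: 5.3% to 6.5% in separate runs. By formula, (2 × 0.5 × 0.2 / 9) / 1.056 = 0.021.
- A 0.5 shift in both measures in the pre-TMS scores only: about 7% to 9%.

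**Random effects.** If 40% of within-subject variance lies at visit level, the visit term alone leaves about 6% to 7% false positives. With a visit-within-subject random intercept as well, the rate is 4.4% to 4.7%.

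**TMS contrasts.** Condition by time uses the change within each visit. A shift common to pre and post cancels, and a visit effect on the change itself is spread over conditions by the randomised order. In simulation (effect 0.40 SD of the difference in change) bias was at most 0.011. Power without visit terms, against with visit and visit by time, was:
- no shift: 80.6% against 79.1%;
- level shifts of 0/0.35/0.5: 79.3% against 79.5%;
- level shifts of 0/0.7/1.0: 74.7% against 79.8%.

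The exception is loss that depends on condition. With an assumed 30% loss after one active condition, complete sets only and practice that differs from pre to post, condition by time was off by 0.030. A visit term removed nearly all of that (0.004 left).

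**The case against.** The case against is substantial. The SAP is one paragraph listing variables of interest, so the absence of a visit term may be brevity. The bias needs three things together: the symptom score is the per-visit VAS, the VAS shifts by visit, and the IDT shifts too. Support for the second is a risk statement about anxiety, which is one of eight VAS items. Participants are asked about symptoms at every visit, and required medication stability argues against gradual drift. For the third there is only plausibility. The 14% and 38% figures need joint, equal and sustained steps of 0.5 to 0.7 SD. All of this stands, and it limits the importance of the point.

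It can also be argued that if the interview raises anxiety and anxiety worsens timing, that covariation is what Aim 2 seeks. This stands in part. But a shift common to everyone at Visit 1 cannot be told apart from first-visit unfamiliarity or fatigue after the interview. Variation between and within patients that is not tied to visit number remains available to estimate the slope.

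A reader might infer that the missing term also biases the TMS effects. The documents do not support that: order is randomised and each visit has its own pre-TMS score.

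**Conclusion.** The point holds conditionally and is of low to moderate importance. As written, the IDT-symptom model could pick up a visit shift shared by the IDT and the VAS. How far is unknown, because the documents give no shift sizes: negligible at joint Visit 1 steps up to about 0.3 within-subject SD, and material at 0.5 or more. These figures rest on 50 patients, an assumed intraclass correlation of 0.6 and equal steps in both measures.

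It would go too far to conclude that any association found will be an artefact, or that the SAP excludes visit: no passage shows the IDT shifting, and visit is simply not mentioned. For the TMS condition by time contrasts only some precision is at stake, provided completing all three visits does not depend on condition. That proviso matters because Protocol III says only complete three-visit data sets can be used.

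**What to change.** In the IDT-symptom model, add visit within protocol (1, 2, 3) as a categorical fixed effect, with random intercepts for subject and for visit within subject. State that the symptom score is the VAS taken at the same assessment as the IDT. Visit is already recorded, so this needs one or two SAP sentences and no new data.

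The fixed effect costs 2 degrees of freedom and no material power in the association model (about 72% with or without it, at an assumed slope of 0.15).

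Adding visit to the other mixed models is reasonable. Visit by time there is best kept as a sensitivity analysis: visit and visit by time together use 4 of 245 residual degrees of freedom (300 scores − 50 subjects − 5 fixed-effect terms) and cost about 1 to 1.5 points of power if there is no visit effect.

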Theta burst stimulation (TBS) is a very efficient rTMS protocol that uses high frequency rTMS burst with lower stimulus intensity, smaller number of pulses and much shorter train duration, yet capable of facilitating longer-lasting post stimulation effects compared with traditional rTMS^{104, 105}. TBS was developed in 2004, based on the physiologic pattern of neuronal firing found in the hippocampus of animal¹⁰⁴. The basic element of TBS contains a three-pulse burst at 50 Hz given every 200 milliseconds (i.e. at 5 Hz). By using this basic pattern, two major TBS paradigms were developed: continuous theta burst stimulation (cTBS, inhibitory) and intermittent theta burst stimulation (iTBS, excitatory), as shown in **Figure 1**. The stimulus intensity required for TBS (80% of active motor threshold –AMT) is lower than that for traditional rTMS protocols, which use 100 to 120% of the resting motor threshold (RMT). Of

note, not only the percentage is less, but the AMT is also of lower intensity than the RMT. Consecutive sessions of TBS have been safely administered in SZ^{103, 106-108} and in BP¹⁰⁹⁻¹¹².

Figure 1: Continuous and Intermittent TBS protocols (from Chung et al., 2015)

In this study, we will administer TBS to the cerebellum in psychosis patients (schizophrenia, schizoaffective disorder, and psychotic bipolar disorder) to investigate with causal explanatory power the role of the cerebellum in time perception abnormalities, executive dysfunction, and mood and psychotic symptoms, which are prevalent in these disorders. We will determine whether modulating (exciting or inhibiting) the cerebellum with TBS leads to changes in (1) time perception (measured by the interval discrimination and repetitive finger tapping tasks) (2) executive function (measured by the N-back, flanker task and multi-source interference tasks), and (3) mood and psychotic symptoms (measured by visual analogue scales). Finally, we will test the hypothesis that time-perception abnormalities mediate, at least partially, the myriad clinical manifestations (i.e., cognitive, mood, and psychotic symptoms) in these disorders. Testing the hypothesis that the cerebellum contributes to the diverse symptoms in psychotic disorders, possibly through a common impairment in time perception, will provide insights that will enable development of more effective therapies that treat the full syndromes, rather than select symptoms.

II. SPECIFIC AIMs:

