The cerebellum plays a major role in information processing but it has not been considered a treatment target for studies of major mental illness. The goal of this study is to investigate the impact of modulating cerebellar activity on mood and psychotic symptoms in patients as well as the closely related domains of executive function and time perception. We will study up to 100 healthy subjects and up to 100 psychosis patients (i.e., schizophrenia, schizoaffective disorder, and psychotic bipolar disorder). In sham-controlled crossover design, we will present validated cognitive paradigms and clinical measures to subjects before and after TMS. We hypothesize that abnormally reduced activity in the cerebellum contributes to the abnormalities in patients and therefore cerebellar stimulation will normalize outcome measures. The circuitry of the cerebellum is complex and the main projection neurons in this brain region (Purkinje cells) are inhibitory. Therefore, we will test the specificity of our hypothesis by including an "inhibition" TMS condition which we hypothesize will worsen the outcome measures. The specific aims are to:

Aim 1: Investigate the role of the cerebellum in abnormalities of time perception, cognition, and mood and psychotic symptoms by evaluating these functions before and immediately after excitatory, inhibitory, or sham TMS applied to the cerebellum in patients with psychosis and in healthy control participants. Participants will undergo three study visits, one for each of the three TMS conditions. At each study visit, we will measure the following before and after TMS:

- a) **Time perception:** We will measure time perception using a time perception task. *Hypothesis:* Compared with healthy control participants, patients with psychotic disorders will have impaired timing perception (i.e., higher number of errors and/or greater inter-trial variability in the task) both at baseline and after sham TMS. We predict that the abnormalities in patients will further worsen after inhibitory TMS, and improve after excitatory TMS.

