We will test for group differences in demographic and clinical variables using SPSS, using χ^2 and t-tests for ANOVA as appropriate. We will first measure the change (Δ) in each of the pre- and post-TMS assessments at each study visit: i.e. accuracy in time interval discrimination task, accuracy and reaction time (RT) in N-back working memory task, executive function in Flanker task accuracy and RT in repetitive finger tapping task, and accuracy and RT in MSIT. We will then run two-way ANOVA for each outcome measure, with diagnosis (patients vs. healthy controls) and the TMS type (excitatory, inhibitory, or sham) as independent variables. These models will include as covariates sex, age, handedness, medication load, and symptom severities (derived from the clinical scales scores: NAART, PANSS, YMRS, MADRS, PSYRATS, BRIEF-A, BIS-11, and the Fagerstrom Test).

D. Power analysis (e.g. sample size, evaluable subjects)

This is a pilot study. This being the first study of its kind, it is difficult to do a formal power and sample size analysis because we do not have a measure of effect size, but given previous similar studies and our usual rate of loss to follow up, we estimate we will need 50 participants per group for each protocol. Of primary interest to the study is the change (Δ) in outcome measures within the psychosis group. With 50 subjects in the psychosis group, we will have 80% power to detect an effect size of 0.35, which is a moderate effect.

VII. RISKS AND DISCOMFORTS:

Common risks of TMS procedure

Subject may feel twitching of the scalp muscles during stimulation and/or local discomfort (tapping sensation) under the coil. It is possible that the subject may feel a headache after the TMS measurement that is generally caused by keeping the head in the same position for a lengthy period of time and/or by stimulation of the scalp muscles and nerves by the TMS pulses. TMS may also induce nausea in some patients¹¹⁴. The headache or nausea, if present, is typically mild, disappears soon and can be treated by mild over-the-counter analgesics.

Although there are no reports suggesting increased risk for TMS during pregnancy, pregnant women are excluded from this study due to insufficient knowledge of the effects of the strong magnetic fields on the fetus.

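### The IDT-symptom model omits condition x time, so if TMS moves both IDT and VAS as Aim 1 predicts, the symptom slope absorbs part of the shared response; at the plan's effect size the inflation is modest.

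*SAP*

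**What the plan says.** The SAP's Statistical Analyses paragraph gives two mixed-model specifications. For outcomes other than the VAS, the terms are TMS condition, time and "the interaction of condition x time as the primary variables of interest". The next sentence covers the IDT-symptom association: "we will run mixed model regression models with TMS condition and time in addition to symptom score as the primary variable of interest". No interaction is named there, and the protocol's section VI.C gives no model for Aim 2 that would supply it.

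The protocol's Specific Aims predict the same pattern in both variables. For time perception (Aim 1a): "We predict that the abnormalities in patients will further worsen after inhibitory TMS, and improve after excitatory TMS". For symptoms (Aim 1c): "Symptom ratings will improve in the period immediately after excitatory TMS, and worsen in the period immediately after inhibitory TMS", with no significant change after sham. Aim 2 then hypothesises that "performance on the time perception task will correlate with performance on a working memory task as well as with mood and psychotic symptoms".

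On structure, "Participants will undergo three study visits, one for each of the three TMS conditions", with IDT and VAS recorded before and after TMS at each visit. That gives 3 x 2 = 6 records per participant. On size, section VI.D states: "With 50 subjects in the psychosis group, we will have 80% power to detect an effect size of 0.35".

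**The concern.** At the pre-TMS record of a visit the stimulation has not yet been given, so condition is only a label there. An effect that differs between iTBS, cTBS and sham exists only in the post-TMS records, which makes it a condition-by-time effect. Main effects of condition and time remove only part of it.

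If stimulation moves IDT and VAS in the same cells, what is left over in each variable lines up with what is left over in the other. The model has nowhere to put that except the symptom slope. Aim 2 could then report that timing and symptoms are linked when each had merely responded to the same stimulation. The bias runs in the direction that Aim 1 implies, better timing with fewer symptoms, so a reader would have no reason to suspect it.

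**Working it through.** **Inputs.** From the documents: 50 patients, six records each, effect size 0.35, 80% power. Assumed: symptom score is the per-visit VAS; equal shifts d on both measures, in opposite directions for iTBS and cTBS and zero for sham; normal errors with residual SD σ = 1; random intercept only; two-sided 5% test; no IDT-VAS link beyond the shared TMS effect.

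**The plan's own figure.** Read as a standardised pre-post change, power is Φ(0.35 × √50 − z) = Φ(2.475 − z). With z = 1.645 (one-sided 5%) this is Φ(0.830) = 79.7%, which matches the stated 80%. With z = 1.96 it is Φ(0.515) = 69.7%. The documents state neither alpha nor sidedness. This supports reading 0.35 in SD-of-change units but does not prove it, so both readings are carried. Since SD(Δ) = √2 σ, they are d = 0.35 and d = 0.35 × √2 = 0.495.

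**What the main effects leave behind.** The post-TMS shifts are +d (iTBS), −d (cTBS) and 0 (sham). The time effect averages to zero, and the condition effects absorb +d/2 and −d/2. The remainder is −d/2 and +d/2 (iTBS pre, post), +d/2 and −d/2 (cTBS pre, post), and 0 for sham. The sum of squares per person is 4 × d²/4 = d². The VAS has the same pattern with opposite sign, so the cross-product is −d². Random within-person variation contributes about 5σ² per person. Hence:

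- slope b ≈ −d²/(5σ² + d²)
- SE ≈ √((1 − b²)/(5n)), about 1/√250 = 0.063 at n = 50
- rejection rate ≈ Φ(−1.96 + |b|/SE) + Φ(−1.96 − |b|/SE)

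At d = 0.495: b = −0.245/5.245 = −0.0467, |b|/SE = 0.0467/0.0632 = 0.739, and the rate is Φ(−1.221) + Φ(−2.699) = 0.111 + 0.003, or about 11.5%.

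| d (residual SD) | b, formula | b, simulated | rate, formula | rate, simulated |
|---|---|---|---|---|
| 0.35 | −0.024 | −0.024 | 6.7% | 5.9%, 7% |
| 0.495 | −0.047 | −0.046 | 11.5% | 11.5%, 12% |
| 0.7 (hypothetical) | −0.089 | −0.091 | 29% | 30%, 30% |
| 1.0 (hypothetical) | −0.167 | −0.169 | 76% | 76%, 77% |

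With condition x time added, these simulated rates are 4-5%.

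**Random-intercept version (3,000 runs per scenario).** Between-person information adds roughly one more σ² to the denominator: b ≈ −0.245/6.245 = −0.039 at d = 0.495. Simulation gave −0.038 and −0.040 (intraclass correlation 0.5 and 0.8), with rates of 11.3% and 11.2%; adding the interaction gave 5.6% for both. A 200-run REML fit gave a slope of −0.040; that is too few runs to judge rates. At n = 35 (an assumed completer count) the rates were 8.9% and 7.7%.

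**Where the bias disappears or shrinks.**
- Only IDT responds: 4.9% to 5.4%.
- All conditions shift equally: 5.4%, even at 0.8 SD of change.
- Only iTBS works: the left-over sum of squares falls to d²/3. The rate is 5.4% to 6.3% at 0.35 SD of change and 21.7% at 0.8.
- Symptom score measured once: it is constant within a person, so in complete data sets it is orthogonal to condition x time and the omission causes no bias.

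**The case against.** Several points on the other side have force.

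**Which symptom score.** The association sentence does not say. PANSS, YMRS, MADRS and PSYRATS-AH are collected only at the first visit of each protocol, and protocol section VI.C derives symptom severities from the clinical scales. With a once-measured score the problem vanishes. The VAS is still the more natural reading, because the same SAP paragraph says that symptoms are measured by VAS, but the SAP needs to say so.

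**Shorthand.** In a one-paragraph SAP, the sentence may mean the preceding model plus symptom score. That is possible. But the sentence names its terms and the interaction is not among them, so a reader can only follow what is listed.

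**Estimand.** The sponsor may want stimulation-induced co-movement to count. The protocol's background states that "we will test the hypothesis that time-perception abnormalities mediate, at least partially, the myriad clinical manifestations". That is a legitimate interest, but the listed model does not serve it: without adjusting for the exposure, which here is condition x time, the slope cannot separate mediation from two parallel responses.

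**Stylised inputs.** The protocol lists eight VAS items and the SAP calls the scores non-normal. The percentages therefore show the mechanism and its rough scale; they do not forecast this trial's error rate.

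**Stronger readings.** A reader might infer that the Aim 2 test is wrong about 30% or 76% of the time. Those rates need shifts of 0.7 or 1.0 residual SD on both measures, which the documents do not support. A reader might also infer that any success under Aim 1 spoils Aim 2. It does so only if both measures respond differently by condition, and materially so at the plan's effect size only if iTBS and cTBS act in opposite directions.

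**Conclusion.** The omission is in the SAP text and nothing elsewhere in the documents repairs it. If the symptom score is the per-visit VAS and the Aim 1 predictions hold for both measures, the slope is biased in the direction those predictions imply. At the plan's effect size and 50 patients, the type I error is about 6-7% or about 11-12%, depending on the units of 0.35, and about 9% with 35 patients on the larger reading. These figures rest on equal shifts in both measures, normal errors and a random intercept. No link here means no link beyond the shared response to stimulation. For a self-described pilot's second aim this is a modest problem, but worth correcting because the correction is so cheap.

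**What to change.** Add condition x time to the IDT-symptom model, so that the symptom slope is estimated within condition-by-time cells. State that the symptom score is the per-visit VAS, and name the item or items used. Report TMS-induced co-movement of IDT and VAS separately, alongside the Aim 1 condition contrasts. If the sponsor wants that co-movement counted as part of the association, the SAP should say so, and the slope should not be interpreted as a timing-symptom link independent of stimulation.

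The cost is 2 degrees of freedom out of about 250 (50 patients x 5 within-person). No new data are needed. In simulation the corrected model held the error rate between about 4% and 6% in every scenario tried.
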